To define (b), (c) and (d): If at least 1 dose of Cladribine has been administered after end of Year 1, for CLARITY or CLARITY EXT then the participant will be considered starting the second treatment course (year). If at least 1 dose of Cladribine has been administered during the first year of CLARITY EXT after receiving at least 1 dose during the second treatment course of CLARITY, then the participant will be considered starting the third treatment course (year). Individual parent study datasets will be used.

2. Long-term Responder/Non-responder:

a. Primary definition

- **Long-term Responder:** Study participants not requiring DMD 4 years or later following their last dose of IMP, and who did not demonstrate any evidence of disease reactivation based on Investigator assessment of clinical and imaging outcomes
- **Non-Responder:** Study participants requiring DMD less than 4 years following their last dose of IMP or who demonstrate any evidence of disease reactivation based on Investigator assessment of clinical and imaging outcomes.

Computation rules:

Prior/concomitant medication eCRF page and “physician sequential treatment decision questions” eCRF page question 8 and 9 to be used to identify the date of the DMD received.

4 years after last dose of IMP = Last dose of IMP date + 4*365.25 days

Evidence of disease reactivation will be defined by either:

- a) MRI lesions: new T1 lesion or new T2 lesion reported
- b) New Relapse reported
- c) EDSS worsening defined as an EDSS score increase of at least 1 point between 2 consecutive visits of at most 365 days (if 2 consecutive EDSS assessments are separated by more than 365 days then EDSS cannot be used in the criteria and will be considered as missing/not reported).

New relapse, MRI lesions and EDSS worsening will be identified utilizing dates in parent studies for the period between last dose of IMP and end of parent study.

For the period following the end of the parent study until SV1 of Classic study the following source data will be used:

- 1) MRI lesion by the eCRF “frequency stable patient monitoring questions” (fspmq) page,

Q4/Q3. If Q4 is answered “yes” the date will be taken from Q3 and determined if the MRI lesion is before the 4 years since last IMP.

- 2) New relapse will be identified using the eCRF “MS Relapse history” page(hxrelap) Q2.2.
- 3) The EDSS worsening by the eCRF “expanded disability status scale (edssr) for retro data” page.

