All partial dates will be imputed as described in Section 9.5.

Different scenarios considering missing/not collected data are provided in the table below:

DMD required	MRI new lesion	New Relapse	EDSS worsening	Responder (Yes/No/ND)
All are missing				ND
At least one is Yes (with or without missing)				No
All are N (with no missing)				Yes
All are N (with at least one missing)				ND

ND=Not determined

b. Definition B (sensitivity):

- **Long-term Responder:** Study participants not requiring DMD 4 years or later following their last dose of IMP.
- **Non-Responder:** Study participants requiring DMD less than 4 years following their last dose of IMP.

c. Definition C (sensitivity)

- **Long-term Responder:** Study participants who did not demonstrate any evidence of disease reactivation based on Investigator assessment of clinical and imaging outcomes 4 years following the last dose of IMP.
- **Non-Responder:** Study participants who demonstrate any evidence of disease reactivation based on Investigator assessment of clinical and imaging outcomes 4 years following the last dose of IMP.

d. Definition D (sensitivity)

- **Long-term Responder:** Study participants who did not demonstrate any evidence of disease reactivation based on Investigator assessment of clinical outcomes 4 years following the last dose of IMP.

- **Non-Responder:** Study participants who demonstrate any evidence of disease reactivation based on Investigator assessment of clinical outcomes 4 years following the last dose of IMP.

Definition A described above is considered the primary definition and will be used in the final analysis. Definition B (definition A revised, using DMD only), Definition C (definition A revised, using reactivation of disease only), and Definition D (as C but removing MRI criteria) will be also performed as a sensitivity analysis. MRI lesions or retro EDSS information are expected to be missing/not collected/not reported. Additional descriptive statistics will be provided for each of the component used in the definition to assess the validity of the criteria.

3. Subset Types of Subsequent DMDs:

- Platform injectable therapy (Interferon- β [Avonex[®], Rebif[®], Betaferon[®], Extavia[®], Plegridy[®]] or glatiramer acetate [Copaxone[®]])
- Monoclonal antibody disease modifying treatment
- Oral disease modifying treatment
- Other subsequent treatment
- Off-label treatments (drugs not approved by regulatory agencies to treat MS)
- No subsequent treatment

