14.3.5 HDA and long-term responders

Responder rates will be analyzed in HDA patients versus the responder rate in non-HDA patients from the Cohort B population and summarized descriptively for the FAS population.

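### The SAP's Definition A needs four observed negatives to call a responder but one observed positive to call a non-responder, so partly missing records bias the responder rate downward

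*SAP*

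**What the plan says.** SAP 8.2.2 builds Definition A from four items: DMD required, new MRI lesion, new relapse and EDSS worsening. Its table of missing-data scenarios has four rows:

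- "All are missing": ND.
- "At least one is Yes (with or without missing": non-responder.
- "All are N (with no missing": responder.
- "All are N (with at least one missing": ND.

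The section anticipates gaps: "MRI lesions or retro EDSS information are expected to be missing/not collected/not reported". Its computation rules add more. When two consecutive EDSS assessments are over 365 days apart, "EDSS cannot be used in the criteria and will be considered as missing/not reported".

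Definitions B (DMD only), C (reactivation only) and D (C without MRI) are sensitivity analyses with no missing-data table of their own. The section also promises: "Additional descriptive statistics will be provided for each of the component used in the definition to assess the validity of the criteria".

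For the rate itself, SAP 14.3.5 says "Responder rates will be analyzed in HDA patients versus the responder rate in non-HDA patients from the Cohort B population", summarised descriptively on the FAS. It does not say whether ND patients count in the denominator.

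**The concern.** A non-responder can be recognised from one documented event. A responder can be recognised only from a complete record. When items are missing, the two true classes are therefore lost to ND at different rates, and the determined patients are a sample selected partly by outcome.

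Three uses of responder status are affected.

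- **The rate, and the HDA against non-HDA comparison (14.3.5).** A group with poorer MRI or EDSS documentation will show a lower rate even if its true rate is the same.
- **The responder against non-responder comparisons of clinical, MRI and genetic characteristics (14.2.2, 14.2.3, 14.3.6).** All responders have complete records, while non-responders may have incomplete ones. The contrast mixes response with completeness of documentation.
- **The 25% rule in 8.2.2.** A category holding fewer than 25% of participants cancels that subgroup analysis. A responder share lowered by the rule could remove the planned responder subset tables.

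**Working it through.** The documents state no responder rate or missing rate for this endpoint, so there is no plan figure to reproduce.

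**1. The table as written.** Four items, each Yes, No or missing, give 3^4 = 81 patterns. Applying the table, 1 pattern gives responder, 65 give non-responder and 15 give ND.

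**2. Direction.** Let p be the true responder rate, c = P(all four items observed | responder) and d = P(at least one Yes observed | non-responder). Then:

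- rate among determined patients = p·c / [p·c + (1 − p)·d]
- rate with ND in the denominator = p·c
- ND share = p(1 − c) + (1 − p)(1 − d)

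If completeness is unrelated to response, non-responders have complete records with the same probability c, and each of those shows its Yes. Incomplete non-responders with a visible Yes are added, so d ≥ c and the rate among determined patients is at most p. With ND kept in, p·c ≤ p in any case. Under any missingness mechanism, the rate among determined patients cannot exceed the rate among complete records: every complete record is kept, and the only incomplete records added are non-responders.

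**3. Illustrative size.** Every input here is an assumption. True rate 50%; DMD always known; relapse missing 5%; MRI and EDSS each missing with probability m; items missing independently; non-responders positive on each item with probability r = 0.5, given at least one positive.

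c = 1 × 0.95 × (1 − m)². 
d = [1 − (1 − r)(1 − 0.95r)(1 − (1 − m)r)²] / [1 − (1 − r)^4].

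For m = 20%: c = 0.95 × 0.64 = 0.608, and d = [1 − 0.5 × 0.525 × 0.36] / 0.9375 = 0.9055 / 0.9375 = 0.966. The rate is 0.304 / (0.304 + 0.483) = 38.6%.

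| MRI and EDSS missing | c | d | Rate, determined only | Rate, ND kept in (all ND non-responders) | All ND responders | ND share |
|---|---|---|---|---|---|---|
| 20% | 0.608 | 0.966 | 38.6% | 30.4% | 51.7% | 21.3% |
| 50% | 0.238 | 0.909 | 20.7% | 11.9% | 54.5% | 42.7% |
| 70% | 0.086 | 0.864 | 9.0% | 4.3% | 56.8% | 52.5% |

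Varying r from 0.4 to 0.6 moves the determined-only rate to 38–39 / 20–21 / 9% and the ND share to 21–22 / 41–44 / 50–55%. The two bounds contain the true 50% throughout.

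**4. False group difference.** Assume a true rate of 40% in both HDA and non-HDA patients, with independent items, DMD observed in 98% and relapse in 95%. If MRI and EDSS are each 80% observed in one group, c = 0.596, d = 0.916 and the rate is 30.2%. If they are 60% observed in the other, c = 0.335, d = 0.841 and the rate is 21.0%. Completeness alone produces a gap of 9.2 percentage points, and the second group falls below 25%.

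**5. Definitions B to D.** B has one item, so no record can be partly missing; it is unbiased if that item is missing at random. Applying the same table to C and D in the 80% case of step 4, C goes from a true 50.3% to 41.2% and D from 63.2% to 59.6%. The observed-to-true ratios are 0.82 and 0.94, against 0.76 for Definition A (30.2 / 40).

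**6. Complete records only.** Restricting both classes to records with all four items observed returns the true rate when completeness is unrelated to response (40% for a true 40%).

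**The case against.** The table's logic is sound for an any-event composite. One event settles non-response, and absence of events cannot be claimed for items nobody assessed. ND is more honest than calling such patients responders. That stands: the defect lies in how the resulting classes become a rate and a comparison.

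The SAP also offers safeguards. Definition B does avoid the asymmetry, so a reader who inferred that all the sensitivity definitions share it would be wrong. But B describes DMD use, not freedom from disease activity. D drops one of the two items expected to be missing, yet still needs EDSS. Component summaries show how much is missing without correcting the rate. Responder status under A to D is listed among the demographic summaries (11.1), and HDA status among the characteristics compared by response (14.2.2). However, the HDA responder-rate table, 15.2.9.1, has no sensitivity version, and no output title names Definition D.

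Protocol 9.4.1 allows multiple imputation, under both missing-at-random and not-at-random assumptions, and SAP section 7 declares no change from the protocol. The option is discretionary, and the SAP does not specify it for responder status.

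A reader might infer that any missing chart lowers the rate. It does not: a wholly missing record is ND, and if such records are missing at random and ND is excluded, the rate is unchanged (a true 40% stays 40% with 30% of charts absent). If ND stays in, it falls to 28%. A reader might also infer that an HDA difference will be spurious. Nothing in the documents shows that completeness differs by HDA status.

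Finally, the analyses are exploratory and descriptive, and the HDA comparison is tertiary. That limits the consequence but does not make the reported rate right.

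**Conclusion.** The concern holds for partly missing records. The asymmetry is literal in SAP 8.2.2, missing MRI and EDSS are expected there, and no planned analysis repairs the Definition A rate.

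With ND excluded, the downward direction is established when completeness is unrelated to response. It would reverse only if responders had complete records more often than non-responders showed at least one Yes, and the documents give no data on that. With ND kept in, the rate is also too low, provided recorded negatives are true negatives. If sites enter an unreported relapse or lesion as No rather than missing, that pushes the rate up, and the table does not address it.

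The size is not established. The figures of about 39 / 21 / 9% against a true 50% show what the rule can do under stated assumptions. They do not predict what this study will report. A false HDA difference is a possibility, conditional on unequal completeness.

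**What to change.** Amend SAP 8.2.2, 14.3.5 and Table 15.2.9.1 as follows.

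1. Report responder, non-responder and ND counts over all patients in each group, including HDA and non-HDA, and state the denominator of every rate.
2. Give each responder rate with its two bounds: all ND as non-responders, and all ND as responders.
3. Add an analysis in which both responders and non-responders must have all four items observed. Use it for the rate and for the responder against non-responder comparisons.

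Do not make a Kaplan-Meier event-free estimate the main result. If patients are censored at their last documented assessment of any kind, someone never scanned counts as lesion-free. In the scenarios above, the estimate then moves close to the all-ND-responders bound (51–59% across the range of r, against a true 50%). It also cannot supply the responder groups that the clinical, MRI and genetic comparisons need.

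The cost is SAP text, a few programs and a few more tables. The stated uncertainty will be wider. The complete-record sample will be smaller, and it is unbiased only if completeness is unrelated to response, which is why the bounds should stand beside it.

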5.1 Inclusion Criteria

Participants are eligible to be included in the study only if all the following criteria apply:

1. Patients with MS randomized in CLARITY/CLARITY-EXT clinical trial(s) who have received ≥ 1 course of IMP (Cladribine Tablets or placebo).

or

Patients with their FCDE randomized in ORACLE MS clinical trial who have received ≥ 1 course of IMP (Cladribine Tablets or placebo).

Informed Consent

2. Can give signed informed consent, as indicated in Appendix 2 (Study Governance), which includes compliance with the requirements and restrictions listed in the ICF and this protocol. Data will be collected from the medical records of deceased or lost to follow-up patients if consent is obtained by participant's proxy/caregiver/legal representative or if an ICF waiver is in place, if permitted by local regulation and approved by the relevant EC/IRB.

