To evaluate long-term mobility after treatment with an investigational medicinal product (IMP; Cladribine Tablets or placebo) as part of the Phase III ORACLE MS and CLARITY/CLARITY-EXT clinical trials.	Proportion of study participants using a wheelchair (defined as unable to walk beyond approximately 5 meters even with aid, essentially restricted to wheelchair; wheels self in standard wheelchair and transfers alone; up and about in wheelchair some 12 hours a day) the majority of the time in the 3 months prior to Study Visit 1 (SV1) or participants are bedridden any time prior to SV1, determined via: 1) Expanded Disability Status Scale (EDSS) score of 7.0 or higher), or Alternative clinical description data in medical records.	Section 14.1
Secondary		

Objectives	Endpoints (Outcome Measures)	IAP section
To assess the long-term disability status after treatment with IMP as part of the Phase III ORACLE MS and CLARITY/CLARITY-EXT clinical trials for the CLARITY/CLARITY-EXT and ORACLE MS populations.	Proportion of study participants with EDSS of 6.0 or higher as determined by EDSS documentation or alternative clinical description in medical records after last IMP from parent study.	Section 14.2.1
To evaluate differences in clinical characteristics between long-term responders and study participants requiring alternate therapies following treatment with IMP for the CLARITY/CLARITY-EXT and ORACLE MS populations.	Clinical characteristics ^a at Study Visit 1 of long-term responders (defined as study participants who did not demonstrate any evidence of disease reactivation based on Investigator assessment of clinical and imaging outcomes until Year 4 or later following their last dose ^b of IMP and who did not receive disease modifying treatment until Year 4 or later following their last dose ^b of IMP) compared to those of other study participants who started on alternate therapy less than 4 years following their last dose ^b of IMP for the CLARITY/CLARITY-EXT and ORACLE MS populations.	Section 14.2.2

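### No long-term-responder definition requires observation to Year 4, so under sensitivity Definition B a chart that ends early with no DMD recorded can count as a responder

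*SAP*

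**What the plan says.** The endpoint in SAP section 5 describes responders as participants who "did not demonstrate any evidence of disease reactivation based on Investigator assessment of clinical and imaging outcomes until Year 4 or later" after their last dose of IMP and who received no disease-modifying treatment over the same span.

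SAP 8.2.2 turns this into rules:

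- The cut-off is "4 years after last dose of IMP = Last dose of IMP date + 4*365.25 days".
- Definition B (sensitivity) uses DMD only. The responder is "Study participants not requiring DMD 4 years or later following their last dose of IMP", and the non-responder is "Study participants requiring DMD less than 4 years following their last dose of IMP".
- DMD timing comes from the medication page and the physician treatment-decision page, with "question 8 and 9 to be used to identify the date of the DMD received".
- Definition C uses disease reactivation only (MRI lesion, relapse, EDSS worsening). Definition D is C without MRI.
- Under Definition A, a scenario table covers missing data. "All are N (with no missing") gives responder Yes. "All are N (with at least one missing") gives ND. Any Yes gives non-responder. All missing gives ND.
- For EDSS worsening, consecutive assessments more than 365 days apart count as missing.

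On who is included, Protocol 5.1 says "Data will be collected from the medical records of deceased or lost to follow-up patients", subject to proxy consent or a waiver. The full analysis set in SAP 8.1.1 takes all participants who received at least one course of IMP, and there is no per-protocol set.

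**The concern.** Being free of DMD and reactivation until Year 4 is known only for a patient who was watched until Year 4. The rules use the cut-off date to decide whether a recorded event is early enough to count. They never use it to ask whether a patient without an event was followed long enough. A patient whose chart stops at month 18 with nothing recorded has unknown status at Year 4, yet nothing tells the programmer to treat that status as unknown.

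Where this misclassifies, it does so in one direction: unobserved patients enter the responder group. Definition B has its own tables in SAP 17.1 for the primary endpoint and all three secondary endpoints in every cohort, except that the EDSS 6.0 and wheelchair tables carry it as a responder subset. There is also an inconsistency. SAP 14.1 counts death due to MS as a primary-endpoint event, but death has no role in responder status. A patient who died of MS in year 3 with no DMD recorded could appear in Table 15.2.1.1.4 both as a Definition B responder and as an event.

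**Working it through.** The documents give no figure for this point, so there is nothing to reproduce. The check has three parts.

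**1. What the ND logic does for each definition.** Each component is Yes, N or missing. With k components there are 3^k patterns. Those with at least one Yes (non-responder) number 3^k − 2^k, one pattern (all N) gives responder, and 2^k − 1 give ND. The rows for B, C and D assume that the table under A is carried over, which the SAP does not say.

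| Definition | k | Patterns | Non-responder | Responder | ND |
|---|---|---|---|---|---|
| A | 4 | 81 | 65 | 1 | 15 |
| C | 3 | 27 | 19 | 1 | 7 |
| D | 2 | 9 | 5 | 1 | 3 |
| B | 1 | 3 | 1 | 1 | 1 |

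These are counts of patterns, not probabilities. They show where the protection lies. Under A, a patient lost early with no DMD and no relapse, but with MRI or EDSS missing, is ND. The SAP itself expects MRI or retrospective EDSS to be missing. Under B everything turns on one item: if an empty DMD record is coded N, the result is responder whatever the follow-up. The SAP does not say whether an empty DMD or relapse page is N or missing, nor whether a component observed for part of the four years is N or missing. In the baseline HDA rules (SAP Table 1) absence is coded as negative: an undated relapse counts as zero and a missing T2 count as fewer than 9.

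**2. Who can be affected.** SAP 6.2 says no cladribine or blinded dosing was allowed in ORACLE MS after termination in October 2011. Protocol 4.1 starts enrolment in about Q3 2019. From 31 October 2011 to 1 July 2019 is about 7.7 years, so an ORACLE MS patient who reaches Study Visit 1 is well past Year 4.

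No last-dosing date is given for CLARITY-EXT. A rough bound uses SAP 6.2: 96 weeks of CLARITY, a gap of at most 118 weeks, and 96 weeks of extension make 310 weeks, and 310 × 7 / 365.25 = 5.9 years. Protocol section 9 places visits around 10 years after initial treatment, which leaves about 10 − 5.9 = 4.1 years even if dosing ran to the last week. Because the 10 years is approximate, this is indicative only. The exposed group is therefore probably the deceased or lost patients entered from charts alone.

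**3. Possible size under Definition B.** Let f be the share of patients whose record ends before Year 4 with no DMD and who are coded N, and p the responder rate among those observed to Year 4. Then

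reported rate = (1 − f)p + f, and the share of responders not observed to Year 4 = f / reported rate.

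Neither f nor p is in the documents. Both are assumed.

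| p | f | Reported rate | Share of responders not observed |
|---|---|---|---|
| 40% | 1% | 0.99 × 0.40 + 0.01 = 40.6% | 0.01 / 0.406 = 2.5% |
| 40% | 10% | 0.90 × 0.40 + 0.10 = 46.0% | 0.10 / 0.460 = 21.7% |
| 60% | 1% | 0.99 × 0.60 + 0.01 = 60.4% | 0.01 / 0.604 = 1.7% |
| 60% | 10% | 0.90 × 0.60 + 0.10 = 64.0% | 0.10 / 0.640 = 15.6% |

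The formula does not describe Definition A, where most such patients would probably be ND.

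**The case against.** The strongest reply is that the primary definition is largely protected. Only the all-N pattern yields a responder under A, EDSS gaps over 365 days count as missing, and MRI and EDSS are expected to be missing. This stands. A reader might infer that the rules as a whole class an early-lost patient as a responder. The documents do not support that for Definition A.

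A reader might also infer that the HDA comparison and the genetic analysis inherit Definition B's weakness. They do not as listed: in SAP 17.1 the HDA and pharmacogenetic tables have no Definition B version. Definition D has no efficacy table there and appears only among the demographic variables in 11.1.

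It can further be said that B and C are described as revisions of A, and D as a revision of C, so carrying over the ND table is a fair reading. That is reasonable, but it does not settle Definition B, because the table helps only if truncated follow-up is coded missing, and no rule says so.

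The study is exploratory and descriptive, component-level summaries are planned, and the affected group may be small. These points limit the importance of the gap. They do not supply the missing rule.

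**Conclusion.** The gap is real and narrow. None of Definitions A to D requires observation to last IMP dose + 4*365.25 days, while chart-only deceased or lost patients are in the full analysis set. Definition B can count them as responders, with an upward bias. C, and D as far as it is reported, are exposed in the same way if the ND table is not carried over. Definition A is exposed only if all four components are coded N on partial follow-up, which is not excluded.

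The size cannot be derived from the documents. Over an assumed 1% to 10% of patients affected, the Definition B rate rises by 0.6 to 6.0 percentage points when p is 40%, and by 0.4 to 4.0 points when p is 60%. An MS-related death before Year 4 with no DMD recorded could be both a Definition B responder and a primary-endpoint event. That such a death must therefore be a non-responder is a further inference that the endpoint text does not support, since it does not list death as a criterion.

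**What to change.** In the computation rules for Definitions A to D in SAP 8.2.2:

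1. Code a component N only if it was observed through last IMP dose + 4*365.25 days. Otherwise, if no event is recorded, code it missing. A late last contact alone is not enough, because it does not show that MRI or EDSS was assessed during the period.
2. State that the ND rule applies to B, C and D.
3. Class death or loss before Year 4 without an event as ND. Show MS-related deaths before Year 4 separately, and optionally treat them as non-responders in a sensitivity analysis.
4. Report, by definition, the number moved to ND by these rules.

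The cost is a few lines of SAP text and programming, using dates largely collected already. The documents do not show the eCRF, so the team should confirm that a last chart-entry date exists for chart-only patients. The downside is slightly more ND patients.
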